3.2.5 Nivolumab Combined with Ipilimumab Clinical Activity

Multiple clinical studies have evaluated nivolumab combined with ipilimumab at different doses and schedules. Based on Phase 3 data showing improved response and survival over standard of care therapies, nivolumab combined with ipilimumab has been approved in multiple countries for the treatment of patients with unresectable or metastatic melanoma, intermediate or poor risk, previously untreated advanced RCC, microsatellite instability-high or mismatch repair deficient colorectal cancer, and NSCLC. Participants with treatment-naïve Stage IV or recurrent NSCLC, demonstrated that a combination of nivolumab plus ipilimumab therapy improved 3-year OS (PD-L1 \geq 1% HR = 0.79 and PD-L1 < 1% HR = 0.64) and 3-year PFS (PD-L1 \geq 1% HR = 0.81 and PD-L1 < 1% HR = 0.75) compared to chemotherapy. Details of the clinical activity and safety profile of nivolumab and ipilimumab in these various malignancies are provided in the USPI and SmPC.

3.3 Benefit/Risk Assessment

Extensive details on the safety profile of nivolumab, ipilimumab, and BMS-986207, including nivolumab in combination with ipilimumab and nivolumab in combination with BMS-986207, are available in the IBs, and will not be repeated herein.^{7,8,9}

3.3.1 Risk Assessment

TIGIT expression is limited to lymphoid cells, so the principal effects are anticipated to be related to the effects of inflammatory cells in specific tissues. Similar to other immuno-oncology (IO) drugs, a general principle is to monitor for immune-mediated adverse events (IMAEs) in various organ systems. To date, BMS-986207 has demonstrated a safe and tolerable profile based on preclinical studies and clinical data from Study CA020002. The nonclinical toxicology assessment of BMS-986207 has demonstrated an acceptable safety profile, supporting clinical use in oncology patients. In vitro treatment of human mononuclear cells with BMS-986207 did not induce markers of lymphocyte activation or cytokine release. Moreover, there was no evidence for CRS in cynomolgus monkeys treated with BMS-986207. In addition, in Study CA020002, BMS-986207 (up to 1600 mg Q4W) in combination with nivolumab or BMS-986207 (600 mg Q3W) in combination with nivolumab and ipilimumab, demonstrated a safe and tolerable profile. Based on the BOIN design in Study CA020002, BMS-986207 600 mg Q3W in combination with nivolumab 360 mg Q3W plus ipilimumab 1 mg/kg Q6W was considered tolerable.

In combination therapy, BMS-986207 may potentiate IMAEs caused by nivolumab and ipilimumab. The safety profile of BMS-986207 in combination with nivolumab plus ipilimumab is expected to have no new categories of AEs compared to combination therapies with either nivolumab plus ipilimumab or BMS-986207 plus nivolumab. The safety profile of nivolumab plus ipilimumab is characterized by immune-related toxicities such as diarrhea, rash, pneumonitis, liver toxicity, and endocrinopathies. The frequencies and intensities of these events in the combination are variable and depend on the specific doses and schedule used. In the dose levels and schedules selected for use in this study, these events were mostly low grade and manageable with the use of corticosteroids. The frequency and types of IMAEs associated with nivolumab and ipilimumab are similar across multiple tumor types and are further described in the Reference Safety Information in their respective IBs.

Participants who develop IMAEs may require prolonged treatment with high dose corticosteroids and other immunosuppressive agents. This could increase the risk of opportunistic infections. IMAE management algorithms in the protocol recommend antibiotic prophylaxis against opportunistic infections in such situations (see [Appendix 6](#)). Due to the potential risk of exaggerated inflammatory response, participants with auto-immune disorders, who are at risk for flare of auto-immunity, will be excluded.

Whether nivolumab, ipilimumab, and/or BMS-986207 administration increases the risk for contracting severe acute respiratory syndrome coronavirus 2 (SARS-CoV-2) infection or increases the severity or duration of symptoms is currently unknown. This unknown risk must be considered when enrolling a participant. No additional safety monitoring or routine screening tests will be required due to the SARS-CoV-2 pandemic. Participants with recent or acute infections will be excluded or delay start of treatment. If a participant has a confirmed SARS-CoV-2 infection while on study intervention, dose delay or interruption of study intervention is required to meet the criteria for resuming study intervention (see [Section 7.4.2](#)).

The mandated biopsies pose limited risk to the participant, and include discomfort, pain and bleeding. [Section 9.8.1](#) provides guidance on lesions that are appropriate for a research biopsy, and participants who are not able to undergo a biopsy with an acceptable risk can participate in some situations. Because of the need to develop predictive biomarkers for participants treated with BMS-986207 in future studies or the clinical setting, the limited risk of a research biopsy in selected (low risk) participants is considered appropriate. See Table 3.3.1-1 for a summary of risk assessments and mitigation strategies.

Table 3.3.1-1: Risk Assessment

Potential Risk of Clinical Significance	Summary of Data/Rationale for Risk	Mitigation Strategy
Study Intervention(s)		
IMAEs (eg, pneumonitis, colitis, hepatitis, nephritis, endocrinopathy, myocarditis, neurologic and skin AEs)	Nivolumab IB; Ipilimumab IB; BMS-986207 IB	Recommended IMAE management algorithms are included in Appendix 6
Potential Infusion-related Reaction	Nivolumab IB; Ipilimumab IB; BMS-986207 IB	Recommended treatment of infusion-related reactions are included in Section 7.4.4
Study Procedures		
Tumor Biopsy	Limited participant risk including pain, bleeding, and infection	Per institutional protocol/investigator discretion
Phlebotomy	Limited participant risk including pain, ecchymosis, bleeding, and syncope	Per institutional protocol/investigator discretion
Other (if applicable)		
Allergy to Contrast Agent	Potential anaphylaxis	Prophylaxis and/or treatment per institutional protocol/investigator discretion

Abbreviations: AE, adverse event; IB, Investigator's brochure; IMAE, immune-mediated adverse event.

3.3.2 Benefit Assessment

There remains a need to improve long-term outcomes in participants with 1L Stage IV NSCLC. Recent studies using anti-TIGIT antibodies in combination with PD-(L)1 inhibition have shown some clinical benefit in 1L Stage IV NSCLC.^{5,6,27} Data from Study CA020002 demonstrates that BMS-986207 when used in combination with nivolumab plus ipilimumab is safe and tolerable, and provides evidence suggesting some preliminary clinical efficacy in participants with advanced solid tumors. CA020016 is one of the first studies to test BMS-986207 in combination with nivolumab plus ipilimumab in 1L NSCLC, thus its potential benefit is not yet known. However, the combination of nivolumab and ipilimumab is approved in the US for the treatment of adults with metastatic NSCLC expressing PD-L1 $\geq 1\%$ and was recently approved in Japan for the

treatment of patients with unresectable advanced or recurrent NSCLC independent of PD-L1 status.³

3.3.3 Overall Benefit/Risk Conclusion

Taking into account the measures taken to minimize risk to participants in this study, the potential risks identified in association with combination therapy of BMS-986207 with nivolumab plus ipilimumab are justified by the anticipated benefits that may be afforded to participants with 1L Stage IV NSCLC.

An independent Data Monitoring Committee (DMC) will evaluate safety based on all available data with particular attention to: (i) AEs or other safety trends whose character, severity, and/or frequency suggest that participants would be exposed to an unreasonable and significant risk of illness or injury; (ii) new nonclinical data suggesting unreasonable and significant risk of illness or injury. In addition to the DMC, the Bristol-Myers Squibb Company (BMS) Safety Management Team (SMT) routinely monitors for actual or potential issues related to participant safety, including clinical trial data, information from literature and non-clinical toxicology reports, which could result in a change in the medical risk-benefit balance associated with study treatment. In this study, the SMT will also use quantitative approaches for continuous safety monitoring of specific AE signals (eg, Grade 3 to Grade 4 treatment-related AEs) in addition to their standard review of the safety data (see [Section 10.5.1](#)). If a safety signal is detected by the SMT, then an ad hoc DMC meeting may occur to assess the risk/benefit and make recommendations about the safety.

If such evaluation suggests that the risk/benefit profile of the study has become unfavorable to participants, the Sponsor will pause enrollment and/or treatment until further evaluation of data and interaction with the appropriate Health Authority(ies) can take place to discuss potential actions. That may include (but are not limited to) a substantial protocol amendment or termination of the study.

The clinical studies of BMS-986207 have been designed to minimize the overall risk to participants. In Study CA020002, no DLTs were reported in the 6 DLT-evaluable participants treated with BMS-986207 600 mg Q3W in combination with nivolumab plus ipilimumab; thus, this dose was considered tolerable. In comparison to other anti-TIGIT antibodies in development that have a wild type Fc region, BMS-986207 has an inert Fc region that may provide less toxicity in participants when used as monotherapy or in combination with PD-(L)1 or CTLA-4 inhibitors. To minimize potential risks, a lower dose of ipilimumab 1 mg/kg at a 6-week dosing interval will be used, which is also the same dose and dosing interval used in CheckMate 227. All study interventions will occur at infusion centers with medical monitoring and the capability to manage infusion reactions, including anaphylaxis. Complete blood counts and chemistry (including liver enzyme) tests will be carried out prior to administration of study therapy and on a weekly basis during the first 4 weeks of treatment. In addition, complete physical examinations (PEs) will be conducted on Day 1 of each new cycle, along with weekly symptom-directed targeted PEs during the first 4 weeks of treatment.

Please see [Section 7.4.4](#) for treatment algorithm for infusion reactions and [Section 7.4.1](#) for toxicity management of study intervention.

Nivolumab and ipilimumab combinations have a well-defined toxicity profile based on a safety database of patients treated with the combination across multiple tumor types. Multiple dose administration regimens were evaluated and nivolumab plus low-dose ipilimumab at 1 mg/kg was shown to be safe and tolerable. In CheckMate 227, a TRAE was reported in the majority (76.7%) of participants with 1L NSCLC treated with nivolumab plus ipilimumab while Grade 3 to Grade 4 TRAEs were reported in 32.8% of participants. Moreover, a TRAE leading to discontinuation was reported in 18.1% of participants. A pattern of immune-related adverse events has been defined, for which management algorithms have been developed; these are provided in [Appendix 6](#). Most high-grade events were manageable with the use of corticosteroids or hormone replacement therapy (endocrinopathies) as instructed in these algorithms.

Non-live coronavirus disease 2019 (COVID-19) vaccination is considered a simple concomitant medication within the study. However, the efficacy and safety of non-live vaccines (including non-live COVID-19 vaccines) in participants receiving nivolumab plus ipilimumab +/- BMS-986207 is unknown.

Additional details on the safety profile of nivolumab and ipilimumab, including results from other clinical studies, are also available in the nivolumab and ipilimumab IBs.^{8,9}

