Combining immunotherapies has proven to be clinically beneficial in some tumor types, including NSCLC. Study CheckMate 227 recently demonstrated that combining nivolumab (anti-PD-1) and ipilimumab (anti-CTLA-4) was safe, tolerable, and improved survival in 1L Stage IV NSCLC in comparison to chemotherapy. BMS-986207 is a monoclonal antibody to TIGIT, another immune checkpoint inhibitor. In Study CA020002, BMS-986207 (600 mg every 3 weeks [Q3W]) in combination with nivolumab and ipilimumab was tolerable.

This study, CA020016, is a Phase 2, multi-center, randomized study of BMS-986207 in combination with nivolumab plus ipilimumab in comparison to nivolumab plus ipilimumab in participants with 1L Stage IV NSCLC. The purpose of this study is to evaluate the safety and efficacy of BMS-986207 in combination with nivolumab plus ipilimumab in 1L Stage IV NSCLC. It is expected that BMS-986207 in combination with nivolumab plus ipilimumab will improve clinical responses (PFS) in participants with 1L Stage IV NSCLC as compared to those receiving nivolumab plus ipilimumab.

Study Duration: The maximum duration for a participant on-study is 4 years from randomization.

Study Intervention Duration: Each dosing cycle lasts 6 weeks (42 days) for up to 2 calendar years (up to 18 cycles), regardless of dose delays.

Health Measurement/Observation: The study will assess the safety and efficacy (PFS, objective response rate [ORR]) in participants treated with BMS-986207 in combination with nivolumab plus ipilimumab in comparison to nivolumab plus ipilimumab.

Study Visit Frequency: Study intervention will be given Q3W. Two biopsies are required: one prior to starting treatment and a second biopsy 29 days after starting treatment (Cycle 1 Day 29). Physical examination is performed weekly for the first 4 weeks, and then approximately every 3 weeks along with the study intervention administration day. Imaging for tumor assessments is done every 6 weeks for 48 weeks, then every 12 weeks. Safety is monitored continuously throughout the study.

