Abbreviations: AE, adverse event; ALK, anaplastic lymphoma kinase; BMI, body mass index; BP, blood pressure; BRAF, b-rapidly accelerated fibrosarcoma proto-oncogene; CRF, case report form; CT, computed tomography; ECG, electrocardiogram; EGFR, epidermal growth factor receptor; FDA, Food and Drug Administration; FFPE, formalin-fixed paraffin-embedded; FSH, follicle-stimulating hormone; HCG, human chorionic gonadotropin; HIV, human immunodeficiency virus; IHC, immunohistochemistry; IRT, interactive response technology; KRAS, Kirsten rat sarcoma viral oncogene homolog; MRI, magnetic resonance imaging; PCR, polymerase chain reaction; PD-L1, programmed death-ligand 1; PE, physical examination; PS, performance status; ROS-1, c-ros oncogene 1; SAE, severe adverse event; SARS-CoV-2, severe acute respiratory syndrome coronavirus 2; WOCBP, women of childbearing potential.

^a Some of the assessments referred to in this section may not be captured as data in the CRF. They are intended to be used as safety monitoring by the treating physician. Additional testing or assessments may be performed as clinically necessary or where required by institutional or local regulations.

Table 2-2: On Treatment Procedural Outline (CA020016)

Procedure	Cycle 1 ^a Visit Window = -3 Days for C1D1, ± 3 Days for All Others					Each Subsequent Cycle		EOT	Notes ^b 1 Cycle = 6 Weeks
	D1	D8	D15	D22	D29	D1 (± 3 Days)	D22 (± 3 Days)		
Safety Assessments									
Complete PE, Vital Signs, Physical Measurements, and PS	X						X	X	Includes weight, BMI, heart rate, seated BP, temperature, oxygen saturation by pulse oximetry and PS (see Appendix 7). BP and heart rate should be measured after the participant has been resting quietly for at least 5 minutes.
Targeted PE, Vital Signs, Physical Measurements, and PS		X	X	X	X			X	Includes weight, BMI, heart rate, seated BP, temperature, oxygen saturation and PS (see Appendix 7). BP and heart rate should be measured after the participant has been resting quietly for at least 5 minutes.
ECGs	X						X	X	ECGs should be recorded after the participant has been supine for at least 5 minutes, and prior to blood draws.
Concomitant Medication Use	Continuously during the study							X	Record at each visit

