AE and SAE Assessment	Continuously during the study							X	Record at each visit. All AEs (SAEs or non-serious AEs), including those associated with SARS-CoV-2 infection, must be collected continuously during the treatment period. For reporting purposes, all AEs/SAEs must be graded using CTCAE v5. All SAEs must be collected from the date of participant's written consent until 100 days post discontinuation of dosing.

Table 2-2: On Treatment Procedural Outline (CA020016)

Procedure	Cycle 1 ^a Visit Window = -3 Days for C1D1, ± 3 Days for All Others					Each Subsequent Cycle		EOT	Notes ^b 1 Cycle = 6 Weeks
	D1	D8	D15	D22	D29	D1 (± 3 Days)	D22 (± 3 Days)		
Laboratory Tests									
Clinical Laboratory Assessments	X			X		X	X	X	Perform on site/local laboratory testing within 72 hours prior to each dose. For the first treatment visit, labs need not be repeated if they were performed within 72 hours and the results are available and have been reviewed for eligibility. Refer to Section 9.4.4 for the list of laboratory tests to be conducted.
Pregnancy Test (WOCBP only)	X			X		X	X	X	Serum or urine within 24 hours prior to first dose, and then every 3 weeks regardless of dosing schedule.
PK and Immunogenicity Assessments									
PK and Immunogenicity Collections	Refer to PK/Immunogenicity collection table in Section 9.5 for timing of collections								
Biomarker Assessments									
Tumor Biopsy					X				Mandatory on-treatment biopsies (if medically feasible) required for all participants. Biopsy window for C1D29 is ± 5 days. EOT/Progression biopsy is optional.
Biomarker Sample Collections	Refer to biomarker collection table in Section 9.8 for timing of collections.								

Table 2-2: On Treatment Procedural Outline (CA020016)

Procedure	Cycle 1 ^a Visit Window = -3 Days for C1D1, ± 3 Days for All Others					Each Subsequent Cycle		EOT	Notes ^b 1 Cycle = 6 Weeks
	D1	D8	D15	D22	D29	D1 (± 3 Days)	D22 (± 3 Days)		
Tumor Assessments									
Body Imaging	Contrast enhanced CT of the chest, CT/MRI of the abdomen, pelvis, and all other known and/or suspected sites of disease should occur every 6 weeks (± 7 days) starting from randomization for the first 48 weeks, then every 12 weeks (± 7 days) until BICR confirmed disease progression or treatment discontinuation (including treatment beyond progression), whichever occurs later. See Section 9.1.1.1 for further details.								

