Gastrointestinal			
Colitis or Diarrhea	Grade 2	Delay dose	Dosing may resume when AE resolves to baseline
	Grade 3	Permanently discontinue Ipilimumab	Nivolumab + BMS-986207 may be resumed when AE resolves to baseline. If Grade 3 diarrhea or colitis recurs while on nivolumab + BMS-986207, permanently discontinue
	Grade 4	Permanently discontinue	
Renal			
Serum Creatinine Increased	Grade 2 or 3	Delay dose	Dosing may resume when AE resolves to Grade ≤ 1 or baseline value
	Grade 4	Permanently discontinue	
Pulmonary			
Pneumonitis	Grade 2	Delay dose	Dosing may resume after pneumonitis has resolved to \leq Grade 1.
	Grade 3 or 4	Permanently discontinue	
Hepatic			
AST, ALT, or T.bili increased	AST or ALT $> 3x$ and $\leq 5x$ ULN or T.Bili $> 1.5x$ and $\leq 3x$ ULN, regardless of baseline value	Delay dose or permanently discontinue	If the abnormality is not associated with new signs/symptoms of liver inflammation, dosing may resume when laboratory values return to baseline. If AST or ALT elevation and symptomatic liver inflammation (eg, right upper quadrant tenderness, jaundice), then permanently discontinue.
	AST or ALT $> 5x$ ULN or T.bili $> 3x$ ULN, regardless of baseline value	Delay dose or permanently discontinue	In most cases of AST or ALT $> 5x$ ULN, study intervention will be permanently discontinued. If the investigator determines a possible favorable benefit/risk ratio that warrants continuation of study intervention, a discussion between the

Table 7.4.2-1: Adverse Event Criteria for Delay, Resume, and Discontinue of Nivolumab, Ipilimumab, and BMS-986207

Drug-Related AE per CTCAE V5	Severity	Action Taken	Clarifications, Exceptions, and Resume Criteria
			investigator and the Sponsor/Medical Monitor (or designee) must occur and approval from Sponsor/Medical Monitor (or designee) prior to resuming therapy.
	Concurrent AST or ALT > 3 x ULN and T.bili > 2 x ULN, regardless of baseline value	Permanently discontinue	
Endocrinopathy			
Adrenal Insufficiency	Grade 2 adrenal insufficiency	Delay dose	Dosing may resume after adequately controlled with hormone replacement.
	Grade 3 or 4 adrenal insufficiency or adrenal crisis	Delay dose or permanently discontinue	Mandatory discussion with and approval from the Sponsor/Medical Monitor (or designee) needed prior to resuming therapy. If adrenal insufficiency resolves or is adequately controlled with physiologic hormone replacement, participant may not require discontinuation of study drug.

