9 STUDY ASSESSMENTS AND PROCEDURES

- Study procedures and timing are summarized in the Schedule of Activities ([Section 2](#)).
- Protocol waivers or exemptions are not allowed.
- All immediate safety concerns must be discussed with the Sponsor immediately upon occurrence or awareness to determine if the participant should continue or discontinue treatment.
- Adherence to the study design requirements, including those specified in the Schedule of Activities ([Section 2](#)), is essential and required for study conduct.
- All screening evaluations must be completed and reviewed to confirm that potential participants meet all eligibility criteria before randomization. The investigator will maintain a screening log to record details of all participants screened and to confirm eligibility or record reasons for screening failure, as applicable.
- Procedures conducted as part of the participant's routine clinical management (eg, blood count) and obtained before signing of informed consent may be utilized for screening or baseline purposes provided the procedure meets the protocol-defined criteria and has been performed within the timeframe defined in the Schedule of Activities ([Section 2](#)).
- Images will be submitted to a central imaging vendor for BICR at any time during the study. Prior to scanning the first participant, sites should be qualified and understand the image acquisition guidelines and submission process as outlined in the CA020016 Imaging Manual provided by the central imaging vendor.
- Perform additional measures, including non-study required laboratory tests, as clinically indicated or to comply with local regulations. Laboratory toxicities (eg, suspected drug induced liver enzyme evaluations) will be monitored during the follow-up phase via on-site/local labs until all study drug-related toxicities resolve, return to baseline, or are deemed irreversible.
- Evaluate participant immediately to rule out cardiac or pulmonary toxicity if participant shows cardiac or pulmonary-related signs (hypoxia, abnormal heart rate or changes from baseline) or symptoms (eg, dyspnea, cough, chest pain, fatigue, palpitations).

Some of the assessments referred to in this section may not be captured as data in the eCRF. They are intended to be used as safety monitoring by the treating physician. Additional testing or assessments may be performed as clinically necessary or where required by institutional or local regulations.

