9.4 Safety

Planned time points for all safety assessments are listed in the Schedule of Activities.

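### Section 3.3.3 cites weekly blood counts and chemistry in the first 4 weeks as a risk-minimizing measure, but Table 2-2 schedules laboratory panels in Cycle 1 only at Day 1 and Day 22

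*Combined protocol and SAP*

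**What the plan says.** Section 3.3.3 (Overall Benefit/Risk Conclusion) lists the steps taken to keep risk low. On laboratory monitoring, it lists blood counts and chemistry with liver enzymes and says that these "tests will be carried out prior to administration of study therapy and on a weekly basis during the first 4 weeks of treatment". It names weekly symptom-directed examinations over the same 4 weeks as a separate measure.

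Table 2-2 (On Treatment Procedural Outline) sets the row Clinical Laboratory Assessments at Cycle 1 Day 1 and Day 22, at Day 1 and Day 22 of each later cycle, and at end of treatment. Its note ties the tests to dosing: "Perform on site/local laboratory testing within 72 hours prior to each dose". Days 8, 15 and 29 are blank in that row. The row "Targeted PE, Vital Signs, Physical Measurements, and PS" is marked at Cycle 1 Days 8, 15, 22 and 29.

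On which text governs, Section 9.4 says "Planned time points for all safety assessments are listed in the Schedule of Activities". Section 9 says that adherence to the design requirements, including that schedule, "is essential and required for study conduct". The Protocol Summary describes only the examination as weekly: "Physical examination is performed weekly for the first 4 weeks".

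**The concern.** The benefit/risk section describes laboratory monitoring that the governing schedule does not require. A site following Table 2-2 will draw a panel before the first dose and the next one before the second dose, three weeks later. Ethics committees and regulators who approve the protocol will read Section 3.3.3 as a commitment to weekly panels.

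The measure has a clear purpose. Section 3.3.1 lists liver toxicity among the characteristic immune-related toxicities of nivolumab plus ipilimumab and says that BMS-986207 may potentiate such events. The hepatic row of Table 7.4.2-1 works from AST, ALT and bilirubin values and expressly allows for a rise without symptoms: "If the abnormality is not associated with new signs/symptoms of liver inflammation, dosing may resume when laboratory values return to baseline". A weekly targeted examination cannot be relied on to find such a rise. Amendment 02 also removed the safety lead-in, and Section 3.2.2.6 reports 7 participants treated at this dose of the triplet.

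**Working it through.** The plan gives no numerical figure to reproduce. The check sets the two texts side by side and counts days.

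**Step 1. Compare the stated and scheduled panels.** Inputs: Section 3.3.3, Table 2-2 and the PK schedule in Table 9.5-1. A cycle is 42 days, so Cycle 2 Day 1 is Day 43.

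| Day | Weekly panel under Section 3.3.3 | Laboratory row, Table 2-2 | Targeted examination, Table 2-2 | PK blood, Table 9.5-1 |
|---|---|---|---|---|
| 1 | yes | yes | no | yes |
| 8 | yes | **no** | yes | yes |
| 15 | yes | **no** | yes | yes |
| 22 | yes | yes | yes | yes |
| 29 | if counted in the first 4 weeks | **no** | yes | yes |
| 43 | pre-dose only | yes | no | yes |

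**Step 2. Confirm that the laboratory row is read correctly.** Three checks agree.

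- The pregnancy-test row has the same marks as the laboratory row, and its note reads "Serum or urine within 24 hours prior to first dose, and then every 3 weeks regardless of dosing schedule". Its two Cycle 1 marks are therefore Days 1 and 22.
- BMS-986207 or placebo and nivolumab are given every 3 weeks, so the Cycle 1 dosing days are 1 and 22. These are the only days that the laboratory note calls for.
- The row has five marks: Day 1, Day 22, later Day 1, later Day 22 and end of treatment. A weekly schedule would add at least Days 8 and 15, giving 5 + 2 = 7. The count alone rules out weekly testing, whatever the column alignment.

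**Step 3. Compute the gaps between scheduled panels.**

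- Day 1 to Day 22: 22 − 1 = 21 days. With Days 8 and 15 added: 7, 7 and 7 days.
- Day 22 to Day 43: 43 − 22 = 21 days. With Day 29 added: 7 days, then 14 days.
- Later cycles: 21 days either way.

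**Step 4. Look for another provision that requires the weekly panels.** Section 9.4.4 asks for results to be reviewed before dosing and sets no weekly panel. Footnote b of Table 2-2 and a bullet in Section 9 allow or direct extra tests when clinically indicated. Neither makes a weekly panel routine for a participant without symptoms.

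**Step 5. Size the change if weekly tests are intended.** Panels to add per participant: 2 (Days 8 and 15), or 3 with Day 29.

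- About 180 randomized participants: 180 × 2 = 360 and 180 × 3 = 540.
- Arm A (120): 240 to 360. Arm B (60): 120 to 180.

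These are upper bounds, because they assume that everyone randomized is treated and attends each visit.

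**The case against.** The strongest reply is that the gap affects no dosing decision. No study drug is given between Day 1 and Day 22, and Table 7.4.2-1 sets rules for delaying, resuming and stopping doses. A Day 8 or Day 15 value could not lead to a delayed dose before Day 22, and the Day 22 dose has its own panel and required review. This stands. A reader might infer that the second dose is given without laboratory protection, and the documents do not support that. What remains is earlier detection and management of a symptom-free rise, which the documents do not allow us to quantify.

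A second reply is that the sponsor may never have intended weekly panels. The laboratory note, Section 9.4.4 and the Protocol Summary all lack them. The documents do not settle the intent. So the panels count as missing only if weekly testing was meant; otherwise the error lies in Section 3.3.3 and no panel is missing. Either way, the two texts cannot both stand.

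A third reply concerns context. In the Phase 1/2a study, all treatment-related events at this triplet dose were Grade 1 or 2 (AST increase and ALT increase in 1 participant each), with no DLT in 6 evaluable participants. A further 30 participants had received BMS-986207 with nivolumab. Weekly targeted visits are scheduled, and extra tests are available when indicated. These facts lower the stakes, but they do not make the sentence in Section 3.3.3 true.

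Two stronger readings should be set aside. A reader might infer that the DMC's early tolerability review of the first 8 Arm A participants is undermined. Sections 5.1.4 and 10.5.1.2 do not tie that review to a number of panels, and the formal boundary in Section 10.5.1 uses Grade 3 to 4 treatment-related events over 12 weeks. A reader might also infer that the benefit/risk conclusion fails without weekly panels. Section 3.3.3 also lists the DMC, monitoring by the Safety Management Team, low-dose ipilimumab every 6 weeks, infusion-center monitoring, physical examinations and management algorithms.

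**Conclusion.** The inconsistency is real, lies in current protocol text and should be corrected. Confidence in the mismatch is high. Section 3.3.3 promises panels 7 days apart in the first 4 weeks, and the governing schedule gives panels 21 days apart. Days 8 and 15 have no panel, and neither does Day 29 if it is counted.

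The effect is confined to safety monitoring in Cycle 1, mainly between the first two doses. Dosing decisions remain covered and PFS is unaffected. The conclusion rests on two points: Table 2-2 governs, as Sections 9 and 9.4 say, and provisions that leave extra tests to clinical need do not amount to a weekly schedule. The number of missed or delayed detections cannot be estimated from the documents, and none is claimed.

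**What to change.** **If weekly panels are intended:** in Table 2-2, row Clinical Laboratory Assessments, add a mark at Cycle 1 Day 8 and Day 15. Add a note that these panels cover hematology and chemistry including liver enzymes. Add Day 29 on the same terms if the sponsor counts it in the first 4 weeks; the targeted examinations, described for the same 4 weeks, already include that day. The note should also say whether TSH is repeated at these visits, because Table 9.4.4-1 lists it under chemistry.

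The cost is two or three marks, one note, and at most 2 to 3 extra panels per treated participant (upper bound about 360 to 540 over both arms). Each report needs documented investigator review under Section 9.4.4. No new visit is needed, since all three days already have a targeted examination, PK blood and biomarker blood (Tables 2-2, 9.5-1 and 9.8-1).

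**If weekly panels are not intended:** delete the weekly clause from the laboratory sentence of Section 3.3.3, so that it refers only to testing before study therapy, and leave the other listed risk measures in place. This costs one phrase and no tests, but it gives up a stated safety measure.

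Adding the panels is preferable. It makes the stated measure true and improves detection of symptom-free laboratory toxicity at visits that already take place.
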